#### 6.4 SUBJECT SETS ANALYSED

#### • Screened set (SCR):

This patient set includes all patients who signed the main informed consent. The screened set will be used for patient disposition tables.

#### • Treated set (TS):

This patient set includes all patients who were documented to have received at least one dose of any study medication. The treated set will be used for all demographic and baseline analyses as well as all safety and efficacy analyses (besides the MTD determination).

#### • MTD set:

The MTD set includes all treated patients who are considered evaluable as per CTP, that is, all patients who have completed the required number of administrations of BI 1387446 (and ezabenlimab in arm B) in cycle 1 and who underwent the Echo/MUGA scan in cycle 2 visit 1. In case a patient has not completed the required number of study drug administrations due to DLT(s), he/she will be considered evaluable and included in the MTD set. Patients who cross over from Arm A to Arm B will only be included in the MTD set if they are evaluable in Arm A. The MTD set will be used for the main analysis of the MTD.

## • PK parameter set (PKS):

This patient set includes all patients in the treated set who provide at least one evaluable observation for at least one PK endpoint and no PK relevant protocol deviations. The PK parameter analysis set will be used for all PK analyses.

### • Biomarker analysis set:

Date: 8 Apr 2024, Version 1.0

This patient set includes all patients in the treated set who provide at least one evaluable observation for at least one biomarker endpoint. The biomarker analysis set will be used for any biomarker analysis.

## 6.6 HANDLING OF MISSING DATA AND OUTLIERS

No imputation will be performed on missing efficacy data. Missing baseline laboratory values will be imputed by the respective values from the screening visit. Every effort will be made to obtain complete information on all adverse events, with particular emphasis on potential DLTs.

Potential outliers will be reported and analysed as observed.

Missing or incomplete AE dates will be imputed according to BI standards (9.3).

Handling of missing PK data will be performed according to the current relevant BI standards (9.4). PK parameters that cannot be reasonably calculated based on the available drug concentration time data will not be imputed.

Proprietary confidential information © 2024 Boehringer Ingelheim International GmbH or one or more of its affiliated companies.

In general, missing data not discussed in the BI standards will not be imputed unless required for the following analyses and definitions. Then the rules as described below apply.

### Change of laboratory values from baseline

Laboratory values at baseline: For missing laboratory data at cycle 1 day 1 (before the first administration of any study medication) the data of preceding visits will be used if available.

## Definition of on-treatment period and actual treatment

Date of permanent discontinuation of study medication: All reasonable efforts should be undertaken during the study to obtain the dates of permanent discontinuation of study medication. However, if the date of the very last administration is missing this will be imputed with:

- If only month and year are given, the last day of the month will be used for imputation
- If only the year is given, the 31st of December of this year will be used for imputation

If the imputed date leads to a date that is later than the date of the EOT visit, then the imputed date is the date of the EOT visit. If the imputed date leads to a date that is later than the death date, then the imputed date is the date of death.

## 6.7 BASELINE, TIME WINDOWS AND CALCULATED VISITS

Unless otherwise specified baseline is defined as the time point closest to but prior to the first administration of any study medication. If no time is specified and the date is the same as the first administration date, then it will still be considered baseline if not specified otherwise. If there is no measurement earlier than the first administration of study medication, then no baseline will be derived.

For the analysis of 'Best percentage change from baseline in size of injected lesions' (CTP version 1 and 2) and 'Best percentage change from baseline in size of injected target lesions' (CTP version 3 and later) the derivation of baseline will follow the itRECIST publication, details are given in Section 7.5.2.

Study days and visits will be labelled according to the flowchart in the CTP.

Proprietary confidential information © 2024 Boehringer Ingelheim International GmbH or one or more of its affiliated companies.

## 7. PLANNED ANALYSIS

The labelling and display format of statistical parameters will follow the BI guideline (9.5).

For End-Of-Text (EoT) tables, the set of summary statistics is: N / Mean / Standard deviation (StD) / Min / Median / Max.

For tables that are provided for endpoints with some extreme data, median, quartiles and percentiles should be preferred to mean, standard deviation, minimum and maximum.

For plasma concentrations as well as for all PK parameters the set of summary statistics will also include: arithmetic coefficient of variation (CV), geometric mean (gMean), geometric coefficient of variation (gCV). Furthermore, for PK parameters the following descriptive statistics will be calculated in addition: 10th percentile (P10), 1st quartile (Q1), 3rd quartile (Q3), 90th percentile (P90). For PK parameters, summary statistics will be calculated using the individual values with the number of decimal places as provided by the evaluation program. The individual values as well as the summary statistics will then be reported with three decimal places.

For Bayesian logistic regression model (BLRM) analysis tables, the set of summary statistics is: Mean, StD, Median and quartiles.

Tabulations of frequencies for categorical data will include all possible categories and will display the number of observations in a category as well as the percentage (%) relative to the respective dose cohort (unless otherwise specified, all patients in the respective patient set whether they have non-missing values or not). Percentages will be rounded to one decimal place. The category missing will be displayed only if there are actually missing values.

Sort order for general categorical variables: If categories correspond to the collected categories in the eCRF and the table shells do not explicitly specify the ordering, the "default ordering" defined by the eCRF is to be used in such cases. If categories are derived, the ordering as specified in the table shell document should be used; in general, ordinal data (e.g. categorized continuous data) are to be displayed in ascending order.

Abbreviations (e.g. Wors.) should not be displayed without any explanations. They will be either spelled out in the table or explained in footnotes (whatever is more reasonable from the programming point of view).

If applicable, conversion from days to weeks, months and years will be as follows:

• Weeks = Days / 7

Date: 8 Apr 2024, Version 1.0

- Months = (Days \* 12) / 365.25
- Years = Days / 365.25

## 7.1 DEMOGRAPHIC AND OTHER BASELINE CHARACTERISTICS

Only descriptive statistics are planned for this section of the report.

Proprietary confidential information © 2024 Boehringer Ingelheim International GmbH or one or more of its affiliated companies.

#### 7.2 CONCOMITANT DISEASES AND MEDICATION

Only descriptive statistics are planned for this section of the report.

Concomitant diseases will be coded similarly as adverse events based on the most current Medical Dictionary for Regulatory Activities (MedDRA) version. Concomitant therapies (CTs) will be coded according to World Health Organization Drug Dictionary (WHO DD). CTs will be classified according to the Anatomical Therapeutic Chemical (ATC) classification system. The third ATC level will be used to categorize CTs by therapy type. In situations where a medical product may be used for more than one equally important indication, there are often several classification alternatives. As appropriate, patients receiving CTs with more than one possible ATC level 3 category will be counted more than once. Footnotes will clarify this possible double counting in tables.

#### 7.3 TREATMENT COMPLIANCE

Not applicable as compliance is not recorded in the eCRF. Drug administration is supervised by the study personnel and will be assessed via drug concentrations (PK data) and exposure data.

#### 7.4 PRIMARY OBJECTIVE ANALYSIS

#### 7.4.1 Main analysis

Date: 8 Apr 2024, Version 1.0

The primary endpoints of the trial are the MTD of BI 1387446 as single agent and the MTD of BI 1387446 in combination with ezabenlimab, and the respective number of patients with DLTs in the MTD evaluation period.

The number of patients with DLTs during the MTD evaluation period at each dose level will be presented. Patients who were replaced during the MTD evaluation period will be excluded from the evaluation of the MTD.

The analysis of the MTD in each treatment arm is based on a joint BLRM for both arms guided by the escalation with overdose control principle.

The MTD in each arm is defined as the highest dose that is expected to cause less than 25% risk of the true DLT rate being above or equal to 33% during the MTD evaluation period. Estimation of the MTD will be based upon the estimation of the posterior probability of the incidence of DLT in toxicity categories during the MTD evaluation period for all evaluable patients, i.e. patients in the MTD set as defined in Section 6.4.

Using the joint BLRM model specified in CTP Section 7, tables and bar charts displaying for each dose the posterior probabilities of the true DLT rates being in either the under-toxicity interval, the targeted toxicity interval or the over-toxicity interval will be produced.

The modified principal stratum strategy as defined in Section 6.3 will be applied for handling intercurrent events in the primary objective analysis. The MTD set will be used for the analysis of the primary endpoint.

Proprietary confidential information © 2024 Boehringer Ingelheim International GmbH or one or more of its affiliated companies.

The primary analysis is aligned with the estimands described in the Table 7.4.1: 1 below.

Table 7.4.1: 1 Estimands table for primary objective analysis

Estimand attribute				
Population	Patients with different types of advanced or metastatic cancer (solid tumours)			
Treatment condition(s)	BI 1387446 monotherapy or			
	BI 1387446 in combination with ezabenlimab			
Variable (outcome)	Occurrence of DLTs in the MTD evaluation period			
Handling of intercurrent events	Treatment discontinuation or dose reduction during the MTD evaluation period due to DLT: Composite – patients will be included in the analysis contributing to the analysis with their DLT			
	Treatment discontinuation or dose reduction during the MTD evaluation period due to other reason than DLT: Principal stratum – patients will be excluded from the analysis and replaced			
	
 
Progressive disease during the MTD evaluation period:
 
Principal stratum – patients will be excluded from the analysis and replaced
 
			
	Death during the MTD evaluation period where the death event is not a DLT: Principal stratum – patients will be excluded from the analysis and replaced			
	Any events other than DLT that cause missed visits during the MTD evaluation period: Principal stratum – patients will be excluded from the analysis and replaced			
Summary measure	Posterior probability of the incidence of DLT in toxicity categories during the MTD evaluation period per dose level for all evaluable patients			

Proprietary confidential information © 2024 Boehringer Ingelheim International GmbH or one or more of its affiliated companies.

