2.1.2 Primary endpoint(s)

[figure not shown]
- MTD based on number of Dose-limiting toxicities (DLTs) (for definition of MTD refer to [Section 7](#))
- Number of patients with DLT in the MTD evaluation period

[figure not shown]
Time frame: Arms A, B From start of treatment until end of cycle 1 (3 weeks, MTD evaluation period)

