Since a Bayesian approach is applied, prior distributions f for each of the parameters $\mu_{\alpha_1}, \mu_{\beta_1}, \mu_{\alpha_2}, \mu_{\beta_2}, \mu_\eta, \tau_{\alpha_1}, \tau_{\beta_1}, \tau_{\alpha_2}, \tau_{\beta_2}, \tau_\eta$ and for ρ_1 , and ρ_2 need to be specified. Weakly informative prior distributions were chosen for the μ - and ρ -parameters, prior distributions for the τ -parameters are chosen to represent a small to moderate between-trial heterogeneity (see [Table 7: 1](#)).

Table 7: 1

Prior parameters of the joint model for Arms A and B

Parameter	Prior distribution
μ_{α_1}	N(log(0.5),2)
μ_{β_1}	N(0,1)
μ_{α_2}	N(log(0.5),2)
μ_{β_2}	N(0,1)
μ_{η}	N(0,1)
τ_{α_1}	logN(log(0.25),log(2)/1.96)
τ_{β_1}	logN(log(0.125),log(2)/1.96)
τ_{α_2}	logN(log(0.25),log(2)/1.96)
τ_{β_2}	logN(log(0.125),log(2)/1.96)
τ_{η}	logN(log(0.125),log(2)/1.96)
ρ_1	U(-1,1)
ρ_2	U(-1,1)

The toxicity probabilities $\pi_{1,d1}$, and $\pi_{12,d1,d2}$, of a DLT at each dose/dose combination will be calculated directly from the posterior samples regarding the arm-specific parameters, i.e. including the respective arm-specific random effects per parameter. They will be summarized per arm using the following intervals:

Under toxicity: [0.00, 0.16)

Targeted toxicity: [0.16, 0.33)

Overtotoxicity: [0.33, 1.00]

Prior probabilities of DLTs at different dose levels/dose combinations, as well as the corresponding probability of under-, targeted and overtotoxicity, are shown in [Table 7: 2](#) and [Table 7: 3](#) for the initial weakly informative priors of the joint model for Arms A and B. As can be seen from these tables, the prior medians of the DLT probabilities represent reasonable assumptions on toxicity, and the uncertainty around the medians is large, showing the low amount of information this prior provides.

Prior probabilities in Arm A show that [REDACTED] fulfils the EWOC criterion and is therefore a suitable starting dose for the monotherapy dose finding in superficial lesions. Prior probabilities for Arm B do not allow to start combination dose finding at [REDACTED] without additional data. However, from the data scenarios provided in [Section 10.5](#) and from

[Tables 7: 4](#) and [7: 5](#), it can be seen that with some additional data from the monotherapy dose finding trials, the overdose probabilities decrease [REDACTED] becomes a suitable starting dose. Of note: At time of amending the CTP to version 5.0, Arm B was already started at this dose level.

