Table 7: 2 Prior probabilities of DLTs in Arm A

[REDACTED]								
	[REDACTED]							
[REDACTED]								
[REDACTED]								
[REDACTED]								
[REDACTED]								
[REDACTED]								
[REDACTED]								
[REDACTED]								

Table 7: 3 Prior probabilities of DLTs in Arm B

[REDACTED]								
	[REDACTED]							
[REDACTED]								
[REDACTED]								
[REDACTED]								
[REDACTED]								
[REDACTED]								
[REDACTED]								
[REDACTED]								

In addition, [Tables 7: 4](#) and [7: 5](#) show the prior probabilities for Arm A and B taking into account data from 1381-0001 that has already been obtained by the time of the CTP writing of this trial. The following data from 1381-0001 has been included in the calculations for the tables given below:

Since this data will be included in all BLRM analyses, the prior probabilities given in [Table 7: 2](#) and [Table 7: 3](#) are not used in practice but only the ones shown in the below tables.

Table 7: 4

Prior probabilities of DLTs in Arm A (taking into account data from 1381-0001)

Table 7: 5

Prior probabilities of DLTs in Arm B (taking into account data from 1381-0001)

The BLRM-recommended dose combination for the next cohort is the level with the highest posterior probability of the DLT rate falling in the target interval [0.16, 0.33) among the doses or dose combinations fulfilling the EWOC principle. Per EWOC it should be unlikely (<25% posterior probability) that the DLT rate at the dose combination will exceed 0.33. However, the maximum allowable dose increment for the subsequent cohort will be no more than 100% for each drug.

The MTD may be considered reached in each arm separately if all of the following criteria are fulfilled:

- Next recommended dose by the BLRM = current dose.

- At least 12 patients have been treated in the specific arm.

And at least one of the following criteria is fulfilled:

- The posterior probability of the true DLT rate in the target interval [0.16 – 0.33) of the MTD is above 0.50, OR
- At least 6 patients have been treated at the MTD.

A detailed evaluation of the model using hypothetical data scenarios and operating characteristics is provided in the statistical appendix ([Section 10.5](#)).

The dose finding part of the trial will be analysed once using the hierarchical model described above. A sensitivity analysis of the dose finding part will consist of separate analyses of each dose finding arm using weakly informative priors for each arm.

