# 5. ENDPOINTS(S)

## **5.1 PRIMARY ENDPOINT(S)**

The main objective of this trial is to determine the maximum tolerated dose (MTD) for BI 1387446 as single agent (Arm A) and for BI 1387446 in combination with ezabenlimab (Arm B). The number of patients with Dose Limiting Toxicities (DLTs) during the MTD evaluation period will be used to determine the MTD in each arm.

The primary endpoints are:

- MTD based on number of Dose-limiting toxicities (DLTs)
- Number of patients with DLT in the MTD evaluation period

The MTD is defined as the highest dose with less than 25% risk of the true DLT rate being above 33% during MTD evaluation period. For definition of DLTs, see CTP Section 4.1.4.4.

The MTD evaluation period is defined as the first treatment cycle including echocardiographic/MUGA scan measurements acquired on Day 1 of Cycle 2.

For analyses, the MTD evaluation period will be derived as the time from the first administration of study drug to the start of the second treatment cycle, i.e. in more detail as the time from the first administration of (any) trial medication to the start of the 2nd administration of ezabenlimab or 4th administration of BI 1387446 (whatever from the latter two comes first). In the case that the 2nd administration of ezabenlimab and/or the 4th administration of BI 1387446 are not given, the MTD evaluation period ends 90 days after the last administration.

Patients who were replaced during the MTD evaluation period will not be considered for MTD determination. Patients who experience a DLT will not be replaced. The decision on replaced patients will be collected in a separate file and stored in the TMF. Patients that have not been replaced will be referred to as patients evaluable for MTD determination (MTD set).

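### The SAP defines the MTD by the 25% overdose limit alone and omits the protocol's Section 7 conditions, so read literally it can name a dose that nobody in the arm received

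*SAP*

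**What the plan says.** **SAP.** Section 5.1: "The MTD is defined as the highest dose with less than 25% risk of the true DLT rate being above 33" percent. Section 7.4.1 repeats the rule per arm: "The MTD in each arm is defined as the highest dose that is expected to cause less than 25% risk of the true DLT rate" is at or above 33%. (Above versus at-or-above makes no difference for a continuous posterior.) Neither section limits the MTD to doses given in the arm, sets a minimum number of patients, or provides for an MTD that was not reached. Section 7.4.1 cites protocol Section 7 for the model only.

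**Protocol.** Section 2.1.2 names the MTD as a primary endpoint and adds "for definition of MTD refer to" Section 7. Section 7 introduces its conditions with the words "The MTD may be considered reached in each arm separately if all of the following criteria are fulfilled". In substance there are three:
- The first ties the MTD to a dose being given: "Next recommended dose by the BLRM = current dose".
- The second sets a minimum size for the arm: "At least 12 patients have been treated in the specific arm".
- The third offers a choice: a posterior probability over 0.50 for the target interval, or 6 or more patients dosed at the MTD.

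Appendix 10.5 treats these as the rules for declaring the MTD, both in hypothetical Scenarios 13 and 14 and in the operating characteristics.

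The 25% limit appears in Section 7 in another role, as the filter on doses open to the next cohort: "Per EWOC it should be unlikely (<25% posterior probability) that the DLT rate at the dose combination will exceed 0.33".

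**The concern.** The SAP has turned a filter for the next cohort into the definition of a primary endpoint. The filter says which doses the model would not forbid. It does not say that a dose has been studied.

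The protocol's own text shows the difference. On the prior alone, before any patient is treated, the Arm A starting dose "fulfils the EWOC criterion and is therefore a suitable starting dose". In Scenario 4 of Appendix 10.5 the limit passes doses in Arm B while the starting dose of that arm is still being set. In the scenarios without DLTs the model's recommendation can exceed the 100% step.

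The Section 7 condition that the next dose equals the current dose ties the MTD to a dose actually given, and the SAP drops it. SAP Section 4 records that development was terminated, and protocol 3.3.5 lets the sponsor stop enrolment for that reason, so an arm could end before the conditions are met. The SAP gives no rule for what is then reported as the MTD other than the 25% limit.

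**Working it through.** **Inputs.** The model and priors come from protocol Section 7 and Table 7: 1, with the second arguments of the normal priors read as standard deviations. Of the dose ladder only 50 and 200 µg are legible (Appendix 10.5). I assumed doublings: 50, 100, 200, 400, 800, 1600 µg. The reference dose d1* is redacted. P(over) is the posterior probability that the DLT rate is at or above 0.33.

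**Reproducing the plan's figure.** In Scenario 02 (1 DLT in 1 patient at the starting dose) the protocol gives P(over) = 0.656. The re-fitted model gives 0.661 at d1* = 700 µg, about 0.656 at 800 µg and 0.650 at 1000 µg. Because d1* was chosen to match this one value, the match is a consistency check, not an independent test. Over the same range the model also returns these stated decisions:
- 1/3 at 50 µg: P(over) at 50 µg is 0.298 to 0.290, so no planned dose is allowed (Scenario 03).
- 0/3 at 50 µg and 1/3 at 100 µg: P(over) at 200 µg is 0.313 to 0.277, so no escalation (Scenario 05).
- A further 0/3 at 100 µg: 0.172 to 0.144, so 200 µg is allowed (Scenario 06).

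Reading the second arguments as variances would need d1* near 100 µg. The prior P(over) at 50 µg would then be 0.284, which contradicts the statement that the starting dose meets the limit.

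**Applying the two rules to Arm A** (P(over) at d1* = 700 / 800 / 1000 µg):

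| Data | Highest dose with P(over) < 0.25 (SAP) | Section 7 |
|---|---|---|
| 0/2 at 50 | 400, not given (0.237 / 0.212 / 0.179) | none: 2 patients, fewer than 12 |
| 0/3 at 50, 1/6 at 100 | 200, not given (0.172 / 0.161 / 0.144) | none: 9 patients, fewer than 12 |
| 0/3 at each of 50, 100, 200, 400 | 800, not given (0.248 / 0.203 / 0.134) | none: 12 patients, but next dose is 800, not 400 |

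The first value in the last row is borderline. At d1* = 400 µg, a worse fit (0.681 for Scenario 02), P(over) at 800 µg is about 0.30 and the SAP rule stays at 400 µg, which was given.

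**Arm B.** The 1381-0001 data are redacted. Assuming 0 DLTs in 12 patients for ezabenlimab and d1* = 800 µg, take 0/3 at 50, 100 and 200 µg in Arm A and 0/3 at 50 and 100 µg in Arm B. The SAP rule names 400 µg in both arms (P(over) 0.048 and 0.082), and neither arm received it. For d1* = 400, 800 and 1600 µg the named dose in Arm B is 200, 400 and 800 µg, always above the highest dose given there.

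**How often, if Arm A stopped early.** Take true rates 0.075 and 0.099 at the first two doses (Table 10.5: 2, Scenario 1) and cohorts of 3. After 6 patients without a DLT the rule names an untested dose. The chance of that path is (1 − 0.075)³ × (1 − 0.099)³ = 0.791 × 0.731 = 0.579. For a stop after 12 patients with the criteria unmet, enumeration at d1* = 800 µg gives 39%, 14% and 53% in Scenarios 1, 2 and 3. At d1* = 400 µg it gives 0% in every scenario. Twelve patients is not a clean limit: 0/3, 0/3, 0/3 and 0/6 at 50 to 400 µg, 15 patients, still names 800 µg at d1* = 800 µg.

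**Once the Section 7 conditions are met.** In exact enumeration of Arm A (cohorts of 3, Scenarios 1 to 5, up to 18 patients) the two rules gave the same dose in every declared trial. Backfill can break this. With 1/8, 2/8, 1/8 and 0/6 at 50, 100, 200 and 400 µg (d1* = 800 µg; 8 + 8 + 8 + 6 = 30 patients), Section 7 gives 400 µg. The SAP rule gives the untested 800 µg, at P(over) 0.238.

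**The case against.** The best counter-argument is that Section 7 gives a rule for stopping escalation, not a definition. Its wording is permissive, its last two alternatives refer to the MTD as if already identified, and protocol 3.1 has the SMC use the criterion when recommending that escalation stop. Protocol 3.1 and the synopsis also plan a model-based MTD estimate per arm under overdose control, with no patient minimum, and SAP 7.4.1 follows that line. This stands in part: the protocol supports both readings. But 2.1.2 points to Section 7 for the definition, and Appendix 10.5 declares MTDs under these conditions. The permissive wording leaves discretion once they hold; it does not support declaring an MTD when they fail.

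SAP Section 3 says the plan is based on protocol Section 7. A general sentence does not put omitted conditions back into an explicit endpoint definition.

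It is also true that the consequence is limited. SAP 7.4.1 tabulates DLT counts and posterior probabilities per dose, so a reader would see a named dose with no patients. Protocol 3.1 caps the RP2D at the highest dose investigated. That cap does not cover the MTD.

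A reader might infer that an arm did end early and that a wrong MTD will be reported. The documents do not support this. Termination of development does not show that the criteria were unmet, and planned enrolment was about 34 and 44 patients.

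**Conclusion.** The point holds as a gap between two definitions of a primary endpoint. Read literally, SAP 5.1 and 7.4.1 can report an MTD where the protocol's conditions would not yet support one, possibly at a dose with no exposure in that arm. The main case is an arm that ends with few DLTs before the conditions are met. When they are met, the two rules will usually agree, with occasional exceptions under backfill.

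The omission itself follows from the text alone. The doses and percentages do not: they rest on an assumed ladder, a d1* fitted to one legible value and, for Arm B, assumed ezabenlimab data. The enumeration leaves out backfill and Arm B. The figures show that the rule can misname a dose; they do not estimate how likely that is in this trial. The effect is confined to the reported MTD. It should be corrected, but it does not put the per-dose safety results in doubt.

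**What to change.** Reconcile SAP 5.1 and 7.4.1 with protocol Section 7. State that an MTD is reported for an arm only if the Section 7 criteria are fulfilled, which limits it to a dose given in that arm. Otherwise state that the MTD was not reached, and give the highest dose evaluated, the DLT counts and the posterior interval probabilities per dose.

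The cost is two short wording edits. No new data or model runs are needed, since the per-dose tables are already planned. The drawback is that the report may have to say that the MTD was not reached in one or both arms.
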